7.5.1.4 Relationship of an Adverse Event to Study Treatment

The investigator is to classify the relationship of an AE to the IP using good clinical judgment and the following definitions:

Not Related	The AE is clearly explained by another cause not related to the study product
Probably Not Related	A potential relationship between study product and the AE could exist (ie, the possibility cannot be excluded), but the AE is most likely explained by causes other than the study agent
Possibly Related	The AE and administration of study product are temporally related, but the AE can be explained equally well by causes other than the study product
Probably Related	The AE and use of study product are temporally related, and the AE is more likely explained by study product than by other causes
Definitely Related	The AE and use of study product are related in time, and a direct association can be demonstrated

Adverse events commonly observed in previous clinical studies with PPC-06 include GI disorders, including diarrhea, nausea, and abdominal pain, and flushing. As a class, FAEs are known to have an effect on lymphocyte and eosinophil counts. Reversible lymphopenia and transient eosinophilia are frequently observed with both Fumaderm and Tecfidera treatment.

7.5.1.5 Adverse Event of Special Interest (AESI)

If the subject complains of any kind of neurological symptoms (such as aphasia, clumsiness, weakening of arms and legs or any new neurological signs or symptoms) during the scheduled study visits or at any time point during the study, the subject will be evaluated at the site for any neurological dysfunction. If the site evaluation for neurological dysfunction is positive or equivocal, the subject will be referred to a neurologist for consultation. If the subject is negative for PML after examination by the neurologist, the subject will continue in the study. If required, the PML experts will be consulted to assess and monitor, as the case may be. The study drug will be stopped in the subject only if recommended by the PML expert.

Stopping Rules:

The potential event of PML will be carefully managed by utilizing the below stopping criteria. If one or more of the below criteria are met, study drug will be permanently discontinued and the subject will be scheduled for an ETV followed by Safety Follow-up visits 1 week (\pm 3 days) after the last dose of study drug.

- Lymphocytes <500/mm³ in one reading;
- Lymphocytes <800/mm³ in 3 consecutive visits 4 weeks apart; Lymphocyte count can be repeated in the interim period. If the interim lymphocyte counts are higher than 800/cu.mm, then the PI with concurrence from Medical monitor, will decide if the subjects should stay in the study or discontinued from the study.
- When recommended by the PML expert.

Blood collection for lymphocyte subset & Ab titer can be collected at any study visit if the subject shows signs of PML.

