5.4 Discontinuation of Treatment or Assessments

Subjects can be removed from the study for any of the following reasons:

- AE(s)
- Protocol violation
- Withdrawal by subject (subject voluntarily discontinued study participation)
- Lost to follow-up
- Pregnancy
- Study terminated by sponsor
- Investigator decision
- Non-compliance with study drug (<80% or >120%)
- Loss of ability to freely provide consent through imprisonment or involuntary incarceration for treatment of either a psychiatric or physical (eg, infectious disease) illness
- Unblinding of a subject for any reason

All subjects meeting the above withdrawal criteria are to be evaluated at the safety follow-up EOS visits unless they have withdrawn full consent. The reason for a subject's permanent withdrawal is to be recorded on the appropriate electronic case report form (eCRF). Subjects

who prematurely withdraw from the study for AEs are to be monitored for up to 30 days after the subject stopped study treatment or until the abnormal parameter resolves or stabilizes.

Pregnancies are to be reported to the sponsor or designee within 24 hours of learning of its occurrence, and the pregnancy is to be monitored to determine outcome. Investigators are to document their attempts to contact subjects who are lost to follow-up.

As a class, FAEs are known to have an effect on lymphocyte and eosinophil counts and can have hepatotoxic and nephrotoxic effects at excessive exposures. The following study drug discontinuation criteria are to be implemented to reduce the risk of toxicity for individual subjects and to investigate the time course of recovery of affected safety parameters.

If any of the following criteria are met, study treatment will be permanently discontinued and the subject will be scheduled for an ETV followed by the Safety Follow-up Visit.

- Lymphocytes $<500/\text{mm}^3$ at any visit
- Lymphocytes $<800/\text{mm}^3$ on 3 consecutive visits
- ALT or AST $>8\times\text{ULN}$ on repeat examination (if assumed increase is related to study drug)
- ALT or AST $>5\times\text{ULN}$ for more than 2 weeks on repeat examination (if assumed increase is related to study drug)
- ALT or AST $>3\times\text{ULN}$ and either total bilirubin $>2 \times$ the ULN or International Normalized Ratio (INR) >1.5 on repeat examination (if assumed increase is related to study drug) in presence of normal alk phosphate.

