- ALT or AST $>3\times\text{ULN}$ with concurrent appearance or worsening of fatigue, nausea, vomiting, right upper quadrant pain or tenderness, fever, rash, or eosinophilia ($>5\%$ eosinophils on differential leukocyte count)
- Serum creatinine $>1.5\times\text{ULN}$ on repeat exam (if assumed increase is related to study drug)
- Proteinuria measured as 3+ or above in urine dipstick on 2 consecutive samples, 4 weeks apart
- If advised by the Medical Monitor or PML experts.

Laboratory tests can be repeated earlier than the next scheduled consecutive visit at the investigator's discretion and any associated safety issue should be followed up as per the Investigator's clinical judgment until resolution/stabilization.

Replacement Policy

Subjects who prematurely discontinue from the study after randomization will not be replaced.

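### Protocol Sections 5.4 and 7.5.1.5 disagree on the lymphocyte <800/mm³ stop when an interim count is higher, and on whose advice triggers a PML-related stop

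*Protocol*

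**What the plan says.** Protocol Section 5.4 introduces its list of laboratory and advisory criteria in mandatory terms: "If any of the following criteria are met, study treatment will be permanently discontinued and the subject will be scheduled for an ETV". The list includes lymphocytes below 500/mm³ at any visit and below 800/mm³ "on 3 consecutive visits". Its last item is "If advised by the Medical Monitor or PML experts". A sentence after the list adds: "Laboratory tests can be repeated earlier than the next scheduled consecutive visit at the investigator's discretion". It does not say what a higher repeat value does to the below-800 criterion.

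Protocol Section 7.5.1.5 covers PML in two parts. The first describes the work-up of neurological symptoms (site evaluation, then a neurologist, then PML experts if needed) and ends: "The study drug will be stopped in the subject only if recommended by the PML expert". The second, under its own Stopping Rules label, opens with an equally firm statement: "If one or more of the below criteria are met, study drug will be permanently discontinued". Its criteria are a single lymphocyte reading below 500/mm³, readings below 800/mm³ at three consecutive visits four weeks apart, and a recommendation by the PML expert. The below-800 item allows repeat counts in between. If those exceed 800/mm³, the investigator, with the Medical Monitor's agreement, "will decide if the subjects should stay in the study or discontinued from the study".

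**The concern.** These criteria are the protocol's stated safeguards against lymphopenia and PML, in a drug class it describes as lowering lymphocyte counts (Sections 5.4 and 7.5.1.4). An investigator at any of about 75 sites may look up the rule in either section. If the two give different instructions for the same counts or the same advice, handling of the subject depends on which page was read.

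The situation is foreseeable. Section 7.5.3 calls subjects back within 2 weeks for a repeat test after a significant laboratory shift, so interim counts are built into the design. Entry is allowed from 1000/mm³ (Section 5.3, exclusion 20d), which is 1000 − 800 = 200/mm³ above the threshold.

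There is a possible statistical consequence too. Stopping leads to an early termination visit. SAP Section 11.4 does not treat assessments more than 15 days after the last dose as on-treatment, and SAP Section 9 imputes missing Week 24 values in the primary analysis. The rule a site follows can therefore decide whether a subject's Week 24 value is observed or imputed.

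**Working it through.** No power or error-rate calculation applies, and the plan states no figure to reproduce. The check sets the two sections side by side and applies them to count sequences.

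**Step 1: the rules compared.**

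| Item | Section 5.4 | Section 7.5.1.5 |
|---|---|---|
| Effect of meeting a criterion | Mandatory permanent stop | Mandatory permanent stop |
| Below 500/mm³ | Any visit | One reading |
| Below 800/mm³ | Three consecutive visits | Three consecutive visits, four weeks apart |
| Interim count above 800/mm³ | Repeats allowed; no stated effect | Investigator decides, Medical Monitor concurring |
| Advice that stops drug | Medical Monitor or PML experts | PML expert |

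The below-500 row agrees in substance. The interim-count and advice rows do not. Section 7.5.1.5 is also at odds with itself on the interim count: its opening makes every listed criterion a permanent stop, yet one criterion ends in a decision.

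**Step 2: the below-800 rule applied.** The counts are illustrative assumptions per mm³, not trial data. Neither section defines whether an interim visit is a visit, so Section 5.4 is read both ways.

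| Sequence | 5.4, scheduled visits only | 5.4, interim visits counted | 7.5.1.5 |
|---|---|---|---|
| A. One reading of 480 | Stop | Stop | Stop |
| B. 700 at Weeks 8, 12, 16; no interim count | Stop, Week 16 | Stop, Week 16 | Stop, Week 16 |
| C. As B, with interim 850 at Week 14 | Stop, Week 16 | Not triggered | Investigator decides, Week 16 |
| D. 700 at Week 4, interim 700 at Week 6, 700 at Week 8, 850 at Week 12 | Not triggered | Stop, Week 8 | Not triggered |
| E. As B, with interim 850 at Week 18 | Stop, Week 16 | Stop, Week 16 | Investigator decides, if a count after the third visit is interim |

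The point rests on C under the scheduled-visit reading: mandatory in one section, discretionary in the other. D and E depend on looser readings of visit and interim, so they show only why those words need defining. Counting interim visits does not harmonise the sections. In C, Section 5.4 then asks for nothing while Section 7.5.1.5 asks for a decision, and in D Section 5.4 requires a stop that Section 7.5.1.5 does not.

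**Step 3: the advice rule applied.** If the PML expert recommends stopping, both sections stop drug. If neither adviser does, neither section stops it on this ground. If the Medical Monitor advises stopping and the PML expert does not, Section 5.4 stops drug. Section 7.5.1.5 does not, either in its neurological pathway or in its stopping list.

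**Step 4: does anything else settle it?** Neither section refers to the other, and no precedence is stated. Section 8.10 lets the SAP override the protocol where they differ, but the SAP contains no lymphocyte or PML stopping rule.

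**The case against.** The best defence is that Section 7.5.1.5 elaborates Section 5.4. Section 5.4 already expects early repeats and clinical judgement in following up safety issues, and Section 7.5.1.5 supplies the missing detail on what a higher repeat means. The four-week spacing adds little, because Table 1-1 already places the post-baseline visits through Week 24 four weeks apart. Section 5.4's sentence on repeats also separates them from the next scheduled visit, which favours the scheduled-visit reading. Nor is the discretionary branch left to a site alone: the Medical Monitor must concur, and counts come from a central laboratory.

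Much of this stands, and it narrows the reach of the problem. It does not remove it. Section 5.4 states no exception, so a reader of that section alone has no licence to keep a subject on treatment after three low scheduled counts.

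A reader might also infer that the sentence confining stops to the PML expert's recommendation contradicts the lymphocyte criteria listed after it. The text does not support that. The sentence closes the neurological work-up paragraph, and the lymphocyte criteria are separate triggers under their own label. What remains is the Medical Monitor's absence from the Section 7.5.1.5 triggers.

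A reader might further infer that every subject with repeated counts between 500 and 800/mm³, or every neurological referral, is affected. Sequence B shows otherwise for counts, and referrals diverge only when the two advisers differ as in Step 3.

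**Conclusion.** The two sections conflict on two points: the below-800 criterion when an interim count is above 800/mm³, and the Medical Monitor's power to trigger a PML-related stop. The first rests on reading visits as scheduled visits and interim as falling between them. On that reading, subjects without a higher interim count are treated alike by both sections.

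Two stronger conclusions are not supported. One is that Section 7.5.1.5 lets the subject stay on drug. It speaks of staying in the study. Its place in a list of drug-stopping criteria makes on-drug the natural meaning, but the text does not say so, and that ambiguity is part of what needs correcting. The other is that the conflict distorts the Week 24 comparison. The route to missing data exists, but the documents give no rate of qualifying counts or of adviser disagreement, so neither the number affected nor any imbalance between arms can be computed.

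The case for correction is that a safety rule should read the same wherever it appears. It takes no view on which rule is clinically right.

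**What to change.** Reconcile Protocol Sections 5.4 and 7.5.1.5 into one list, used or cross-referenced in both places. The list should state:

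- whether a higher interim count changes the below-800 criterion, and if so how;
- whether interim visits count towards the three consecutive visits;
- whether staying in the study means staying on study drug;
- whose advice triggers a PML-related stop.

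The opening of the Section 7.5.1.5 stopping list should then match whatever is decided, so that no listed criterion is both mandatory and discretionary. The clinical choices are for the sponsor's safety team. The cost is wording only, by protocol amendment or clarification letter; the sample size and the planned analyses need not change.

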7.5.2 Serious Adverse Event

An SAE is any untoward medical occurrence that at any dose:

- results in death
- is life-threatening
- requires in-patient hospitalization or prolongation of existing hospitalization
- results in persistent or significant disability/incapacity
- is a congenital anomaly/birth defect, or is an important medical event

The death of a subject enrolled in a study is per se not an event, but an outcome. Any event resulting in a fatal outcome must be fully documented and reported, regardless of the causality relationship to the IP.

The term life-threatening refers to an AE in which the subject was at immediate risk of death at the time of the event. It does not refer to an event, which may have caused death, if it was more severe.

Medical and scientific judgment should be exercised in deciding whether expedited reporting is appropriate in other situations, such as important medical events that may not be immediately life-threatening or result in death or hospitalization but may jeopardize the subject or may require intervention to prevent one of the other outcomes listed in the definition above. These should also usually be considered serious. Examples of important medical events include AEs, which suggest a significant hazard, contraindication or precaution, occurrence of malignancy, or development of drug dependency or drug abuse.

Any SAE, whether or not deemed drug-related or expected, must be reported immediately to the sponsor's designee as soon as it becomes known to the investigator and not later than within 24 hours of his/her knowledge of the occurrence of an SAE. The investigator will document such events in the best possible detail on the SAE Report Form to be transmitted to the sponsor's designee.

An IND Safety Report (INDSR) is an SAE that is both unexpected (not consistent with the current Investigator's Brochure/product information) and for which there is evidence to suggest a causal relationship between the drug and the AE. The Institutional Review Board (IRB) will be informed of INDSRs according to local requirements. All investigators participating in the trial will also be notified of unexpected SAEs. The sponsor will report SAEs and other events requiring expedited reporting to regulatory authorities as required.

Investigator instructions for reporting SAEs are provided in [Section 13.2](#).

7.5.3 Safety Laboratory Assessments

Blood and urine samples for laboratory tests (hematology, serum biochemistry, and urinalysis) will be collected as specified in [Table 1-1](#). Clinical laboratory specimens will be analyzed by a central licensed and accredited laboratory facility according to the laboratory's standard operating procedures.

If any of the laboratory parameters of interest show a significant shift from baseline, subjects will then be scheduled for an interim visit within 2 weeks to repeat the laboratory measurements.

Non-fasting blood samples will be obtained at each visit for laboratory analysis of serum glucose, lipid panel, hsCRP, and PD study.

No blood is to be collected for the PD study at Screening.

Blood samples for serology assessment (HIV, HBsAg, Anti-HBc, and HCV) will be obtained at Visit 1 (Screening).

Lymphocyte subsets and antibody titer will be collected for safety assessments per [Table 1-1](#).

The routine clinical laboratory tests to be performed are provided in [Table 7-2](#).

The investigator may collect additional blood or urine samples to repeat any laboratory test that was abnormal post-dosing, or was within normal limits at Baseline, and is considered clinically significant. Abnormal laboratory results at the last scheduled visit may require additional collection of samples on an "as needed" basis until: a) the values return to the baseline value, b) the values are within normal limits, c) the values are clinically stable, or d) the investigator determines that further follow-up is unnecessary. The investigator will record the date and time of all additional samples collected. If the investigator establishes a clear explanation for the laboratory abnormality, he/she will record this explanation in the eCRFs.

Blood will also be collected and evaluated for PD study per [Table 1-1](#).

Table 7-2 Routine Clinical Laboratory Assessments

Hematology		
• Platelet Count	RBC Indices:	Automated WBC Differential:
• RBC Count	• MCV	• Neutrophils
• WBC Count (absolute)	• MCHC	• Lymphocytes
• Lymphocytes (absolute)	• MCH	• Monocytes
• Neutrophils (absolute)		• Eosinophils
• Monocytes (absolute)		• Basophils
• Hemoglobin		
• Hematocrit		
• Lymphocyte subset (collected and will be assessed)		
• Antibody titer (collected and stored with assessment done as required)		
Chemistry		
• Sodium	• Creatine Kinase	• Cholesterol
• Potassium	• Alkaline Phosphatase	• Triglycerides
• Chloride	• GGT	• HDL Cholesterol
• Bicarbonate	• LDH	• LDL Cholesterol
• BUN	• Total Bilirubin	• Calcium
• Creatinine	• Direct Bilirubin	• Phosphorus
• AST (SGOT)	• Total Protein	• Uric Acid
• ALT (SGPT)	• Glucose (non-fasting)	• Magnesium
	• Albumin	• Creatinine Clearance
Routine Urinalysis		
• Appearance, color		
• pH, specific gravity		
• Glucose, blood, bilirubin, leukocyte esterase, ketones, nitrates		
• Urine protein, urine creatinine, protein:creatinine ratio		
• Microscopic examination (if indicated per clinical laboratory standards)		
Serology (Visit 1/Screening only)		
• HIV		
• HBsAg and Anti-HBc		
• HCV		

7.5.4 Pregnancy Testing

All female subjects will undergo a serum pregnancy test at the screening visit. Female subjects of child-bearing potential will undergo a urine pregnancy test at the baseline visit before the subject is randomized. If either pregnancy test is positive, the subject will not be permitted to enroll in the study.

Urine pregnancy tests will be performed as per the study schedule. At the investigator's discretion, additional testing for pregnancy may be performed for verification purposes. The

pregnancy tests must have a sensitivity of at least 25 mIU/mL. If there is a suspicion of pregnancy at any time during the study, a urine sample will be obtained and tested. Should a subject become pregnant during the study, treatment must be immediately discontinued. Subjects should continue with non-treatment and/or follow-up visits.

All pregnancies should be immediately reported to the sponsor/Contract Research Organization (CRO)/Medical Monitor and followed through to resolution (ie, delivery, miscarriage, or abortion). The report should be submitted within the same timelines as an SAE (within 24 hours of knowledge), although a pregnancy per se is not considered an SAE.

7.5.5 Vital Signs

Measurements of vital signs, including blood pressure, pulse rate, and respiratory rate, will be taken at every visit with the subject seated.

7.5.6 Physical Examination

A complete physical examination including assessments of the head, eyes, ears, nose, throat, skin, neck (including thyroid), lungs, cardiovascular, abdomen, lymph nodes and extremities will be obtained at Screening. Weight (in kg), height (in cm) and waist circumference (in cm) will also be measured.

An abbreviated physical exam including changes since the Screening Visit with focus on previously noted abnormalities in organ systems, including skin, will be completed at Baseline/Visit 2 and at all post-Baseline visits. Weight will also be measured.

Abnormalities noted during the Screening or Baseline physical exams should be recorded on the Medical History eCRFs. Any abnormalities noted on the physical exam following the first dose of study drug should be recorded as an AE, as appropriate.

7.5.7 Electrocardiogram

A 12-lead electrocardiogram (ECG) will be recorded at the visits specified in [Table 1-1](#).

7.6 Appropriateness of Measurements

The methodology used in this study to determine efficacy and safety are the standardized and most widely accepted methods for evaluating safety and efficacy in studies of plaque psoriasis.

8. STATISTICAL METHODS AND DETERMINATION OF SAMPLE SIZE STATISTICAL AND ANALYTICAL PLANS

8.1 General Considerations for Data Analysis

The methodology presented in this section represents a brief overview of the statistical methods that will be fully detailed in the statistical analysis plan (SAP). The SAP will be finalized before the database is locked and unblinded. Any changes to the methods described in the final SAP will be described and justified in the clinical study report.

Study sites will be pooled into analysis centers for the efficacy analyses. The composition of pooled analysis centers will be finalized before the database is locked and unblinded.

All statistical analyses will be performed using SAS statistical software (Version 9.2 or above). Statistical significance will be tested at the 2-sided 5% level. Subgroup analyses (eg, prior biologic use) may be performed.

Data collected in this study will be presented using summary tables, figures, and subject data listings. Summary tables will present data by treatment group and, if applicable, by time of collection. Continuous variables will be summarized using descriptive statistics, specifically the mean, median, standard deviation, minimum and maximum. Categorical variables will be summarized by frequencies and percentages. Figures will be used to support the presentation of certain data.

